facilitate compliance, assessments are designed to be short, with each assessment requiring less than 3 minutes to complete. For the Full AA conditions, the morning report will include a retrospective report on drinking and transportation the previous day, including drinking location(s), transportation used and options available; social context of drinking episodes (Thrul & Kuntsche, 2015); and intentions/plans for drinking and transportation the Research Strategy Page 67 Contact PD/PI: [name] upcoming evening. For the evening reports, participants will report on their mood, craving, core study variables, current drinking behavior (if any) and AID intentions. When participants do not report drinking, additional “filler” questions on current mood will be assessed to equalize time to complete the report. For

the MA control condition, participants will complete abbreviated versions of each report, with no questions

specific to AID. The morning report will ask about drinking location, transportation, and social context the previous day, with no questions on plans/intentions. The evening reports will assess mood, craving, core study variables (except for AID attitudes), and current drinking behavior. In addition to the four core constructs, the EMA Evening Assessments will also include: Mood. Questions from the Positive and Negative Affect Schedule (PANAS-X; Watson & Clark, 1999); Alcohol craving. Using a single 100-point visual analog scale, asking “How much do you want a drink right now?”; Social Context. Participants will be provided a list of who they are currently with and asked to check all that apply, including 1) romantic partner, friend, coworker, child(ren), parent, other family, someone else. This measure is used in EMA studies of drinking behavior by Co-investigator [name] (Lane et al., 2015); AID Intentions. Will be assessed at each evening assessment for those in the Full AA conditions.

Transdermal Alcohol Concentration (TAC). TAC measurement will be taken continuously by the Skyn. All participants will be asked to wear

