their Skyn throughout the AA assessment period, but particularly during drinking episodes. A change in the revised application is that participants will not be able to see their current TAC at any time. However, for participants in the Full AA conditions, once the Skyn registers that they have reached .05 g/dl TAC, the app will prompt them to consider alternative transportation. Clickable links for local taxi/ride services will also be presented. Participants will be told that this prompt is based on their current TAC, and that it indicates it is not safe for them to drive, but will not be told the TAC trigger for this prompt. As noted, participants will wear the Skyn during their laboratory alcohol session. This will allow us to collect data on the accuracy of the Skyn's TAC estimates and, if necessary, develop individualized algorithms for estimating BrAC from TAC. Geospatial data. Throughout the AA assessment, participant location and movement data will be passively recorded on the study-provided smartphone. At the end of the AA period, this data will be combined with EMA data. When a participant reports drinking (or records a positive TAC), information about their drinking location, distance from home, travel using a motor vehicle, and what time they

returned home will be recorded. The most recent evidence for the accuracy of cellphone GPS systems indicate sufficient precision for our proposed use (Zandbergen & Barbeau, 2011). Using a much earlier generation of smartphones, they concluded that position estimation errors were uncommon, for example finding that horizontal location errors ranged from 5-21 meters in the least ideal conditions (static indoor testing). Data were more precise when moving outdoors, due to the clearer access to satellite data. Based on

this, we will use this geospatial information to provide a validity check on participant self-report. Discrepancies between participant selfreported location, use of motor vehicle, etc., will be probed during their next TLFB interview. As noted, [name] will provide the project with a database of GPS locations for all nearby licensed drinking establishments

Statistical Analyses and Power:

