Aim 1. Integrating laboratory and event-level predictors of AID. For Aim 1, we will employ a two-part (hurdle) model to test laboratory and AA predictors of AID. Part one of the model examines predictors of engagement in AID (or driving after any drinking). For this part of the model, we will employ a mixed logistic model examining factors that are predictive of a dichotomous variable indicative of whether, for a given drinking event, a participant drives after drinking alcohol. The second part of the model will employ a Gaussian linear mixed model, and examines predictors of a participant's TAC/BrAC level at the time of driving for drinking events where driving is reported. This analytic approach provides us with both increased flexibility and precision in our analyses. For example, we will be able to identify predictors of driving after any drinking as well as predictors that may be specific to driving at higher TAC. We believe that this flexibility is an important improvement to our approach in the revised application. For example, Hypothesis 1.3 will examine whether contextual factors increase the influence of AID risk factors on the likelihood of AID. Hypothesized contextual factors are based on studies demonstrating that drinking location (fewer miles to home; Kelley-Baker et al., 2013) and venue (drinking in restaurants; Gruenwald et al., 2002) are associated with increased AID risk. Our two-part model will allow us to test whether, for example, drinking venue increases the effect of AID risk factors for driving after any drinking, while drinking location increases the effect of AID risk factors when predicting driving at higher TAC/BrAC. In addition to examining TAC/BrAC at time of drinking as a continuous attribute, our approach will allow us to examine rational cutpoints for TAC – specifically, we will test models for cutpoints of TAC/BrAC of the current U.S. legal limit (.08) and NHTSA's proposed limit (.05). Research Strategy Page 68 Contact PD/PI: [name] Both models will have two levels, comprised of drinking events within participants. We will estimate models via both Maximum Likelihood methods and Generalized Estimating Equations; the former method can result in more accurate parameter estimates in certain situations (Stroup, 2013), whereas the latter method can be more flexibly extended to assumption violations (e.g., variance heterogeneity). Modeling will proceed by first fitting baseline GLMMs that establish associations between lower-level measures and the DV. The lower-level measures will be at the event level (including such variables as drinking venue), so they will directly address Hypothesis 1.2. Once these lower-level associations are established, we will then incorporate laboratory measures to address Hypothesis 1.1, followed by interactions to address Hypothesis 1.3. For example, consider studying the relationship between event-level impulsivity and AID. We will first person-center the impulsivity variable, so that the associated regression weight provides information about the effect of impulsivity as a participant departs from his/her mean level of impulsivity. We will then establish an association between impulsivity and AID using a two-level logistic model, where multiple eventlevel variables are included as IVs. The models will account for individual differences in associations between the event-level variables and AID, and they will be further extended (using level-2 IVs and cross-level interactions) to study the laboratory-based effects and moderation effects from Hypotheses 1.1 and 1.3. We will fit multiple versions of the models using different subsets of IVs, in order to establish that effects are robust to choice of predictors. This is important because unmodeled heterogeneity (resulting from omitted predictor variables) can adversely impact model estimates (Mood, 2009). To estimate power associated with these models, we adopted a simulation-based approach (Gelman & Hill, 2007). This involved generating artificial data from an assumed true model, fitting the proposed GLMM to each artificial dataset, and computing power based on the results. To estimate our power to detect an association between event-level impulsivity and AID, we specified parameter values for the true model based on previous studies. First, based on pilot data, we assumed that participants report driving following 15% of drinking events. We also assumed that each 5- point increase in impulsivity (as measured by delay discounting) was associated with (i) a 10% increase in the odds of driving after drinking (the low end of observed effect sizes for core study constructs) and (ii) a BrAC increase of .01, with random participant effects included in “maximal” models (Barr et al., 2013). In using these parameter values along with the anticipated sample sizes, our estimated power to detect these

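### The driven-events-only TAC model in Aim 1 cannot by itself show that a predictor is specific to driving at higher TAC

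*Combined protocol and SAP*

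**What the plan says.** Under Statistical Analyses and Power, Aim 1, part one is a mixed logistic model of "whether, for a given drinking event, a participant drives after drinking alcohol". Part two is a Gaussian linear mixed model that "examines predictors of a participant's TAC/BrAC level at the time of driving for drinking events where driving is reported". The plan presents the pairing as a gain in flexibility, because it can identify "predictors of driving after any drinking as well as predictors that may be specific to driving at higher TAC". It illustrates this with Hypothesis 1.3: one contextual factor might act on driving at all, and another on driving at a higher level.

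The text supplied contains no model of TAC over all drinking events and no comparison of TAC between driven and non-driven events. It does not name amount drunk or peak TAC as a covariate. The cutpoint models at .05 and .08 do not state their denominator. Fitting several sets of predictors is described as a robustness check, and no such contrast is mentioned there.

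The data for a comparison will exist. Under Transdermal Alcohol Concentration, "TAC measurement will be taken continuously by the Skyn", for all participants. Under Geospatial data, each reported drinking event or positive TAC yields "information about their drinking location, distance from home, travel using a motor vehicle, and what time they" got home.

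**The concern.** Specificity is a comparative claim. To say that a factor bears on driving at a higher level, and not merely on drinking more, one must know what it does when people drink and do not drive. Part one includes the non-driven events, but only for the yes/no outcome. Part two has TAC as its outcome but drops the non-driven events.

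TAC at driving depends heavily on how much was drunk. A factor that raises drinking equally on every occasion raises TAC on driven occasions by the same amount, even if it has no bearing on the decision to drive. Alcohol demand, one of the four core constructs, is an obvious candidate. If driving does not depend on level, such a factor is null in part one and positive in part two, which is the pattern that invites the word specific. This is not reverse causation: it applies equally to predictors measured sober in the laboratory (Hypothesis 1.1). At stake is whether a general drinking predictor is read as a predictor of the decision to drive impaired.

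**Working it through.** **1. The plan's own figures.** Inputs: "participants report driving following 15% of drinking events" (Aim 1); two driving events per month without AA, and 100 + 100 participants (Aim 2 power text); six weeks of observation (Ambulatory Assessment).

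- Drinking events per month: 2/.15 = 13.3. Over 42/30.4 = 1.38 months: 18.4 per person, of which 2.8 are driven.
- 200 participants: about 3,684 drinking events, 553 driven. The reduced set of 150 (half of 100, plus 100): about 2,763 and 414.

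The stated power of .99 for part two cannot be reproduced, because the predictor SD, TAC SD, random-effect variances and alpha are not given. Assume two-sided alpha .05 and a predictor SD of one unit (5 points). Power is then about Φ(.01 × √553 / SD − 1.96), which gives 1.00, .975 and .84 at TAC SDs of .04, .06 and .08. So .99 is plausible and is not in dispute.

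**2. A factor that only raises drinking, with driving unrelated to TAC.** TAC rises by .01 per unit in every event. Assumed: within-person TAC SD .03 to .06, between-person SD .02; 400 datasets per setting, 200 or 150 participants.

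- Part one: log-odds ratio about 0, significant in 4–7%.
- Part two: slope .0097 to .0101, significant in 93–100% (200 participants) or 82–100% (150).
- Slope in non-driven events: .0099 to .0101, the same.

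With a smaller effect (.005 per SD, 200 × 18 events, SDs .015 between and .03 within), part two was significant in 91–93% for an event-level predictor. For a person-level predictor, such as a laboratory measure, it was significant in 82%.

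**3. Is a drove × predictor interaction on TAC enough?** With driving unrelated or mildly related to TAC, the interaction behaves well for a pure drinking factor (significant in 4–6%). But it conditions on driving, which may depend on TAC. Suppose people drive mainly below a tolerance: P(drive) = .35/(1 + exp[200(TAC − .05)]), about 14% driven (assumed; SDs .015 and .03).

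- Pure drinking factor, +.005: interaction about −.0028, significant in 74–75%, although the driving decision is untouched.
- Factor raising both drinking and tolerance by .01: interaction about 0, significant in 3–5%. A real effect is missed.

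**4. Driving given TAC.** A logistic model of driving, adjusted for event TAC, was significant in 4–6% for pure drinking factors and in all runs for true tolerance effects. Two different truths, each with +.01 on drinking, show why it is needed:

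| | Drinks more; driving at random | Drinks more and tolerates more |
|---|---|---|
| Part one, log-odds | about 0 | about 0 |
| Part two slope | .010 | .010 |
| Slope, non-driven events | .010 | .010 |
| Log-odds of driving at a given TAC | 0 | about .41 |

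Only the last row separates them. (Right-hand column: 500 further datasets under the step 3 model, mean TAC .06. The left-hand zero in the last row follows from driving at random.)

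**5. Form of TAC in that model.** In the same further runs, I took the +.005 pure drinking factor under the tolerance model and added a TAC × predictor term with TAC linear. The product term was then falsely significant in 61–66%, because it absorbed curvature. With TAC as a four-knot restricted cubic spline, it was 5%. Tolerance effects were still detected in all runs.

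**6. Precision of the descriptive contrast.** SE ratio to the drives-only slope: √(1 + .15/.85) = 1.085. Power of .99 corresponds to 1.960 + 2.326 = 4.286; 4.286/1.085 = 3.95; power about .98. This holds only for event-level predictors with equal residual variance and no random interaction slope.

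**The case against.** The plan's sentence is hedged and is offered as an example. In context, specific may mean only related to part two and not to part one. The aim is to test predictors, and for prediction, drinking more before driving is a legitimate route to driving at a higher level. The supplied text is also partial: the full wording of the hypotheses and the work overview it cites are absent, and covariates are unspecified, not excluded. Current drinking is collected in the evening reports. All of this is fair, and it limits the point to interpretation.

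A reader might infer that the hurdle model is invalid, that drinking predictors will inevitably be published as impaired-driving predictors, or that the power is wrong. The documents support none of these. Part two validly describes its stated outcome, the wording is tentative, and the power inputs are not given.

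A reader might also infer that a drove × predictor interaction settles the matter. Step 3 shows that it need not. The plan itself gives reason to expect driving to depend on TAC: in the Full AA conditions the app suggests other transport once TAC reaches .05.

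What remains is that, even on the milder reading, a null part one with a positive part two does not distinguish drinking more from driving at a higher level.

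**Conclusion.** The point holds as a limit on interpretation. The part-two coefficient combines general drinking level with willingness to drive at a higher level, and the planned analyses do not separate them. That follows from the analysis set and does not depend on any assumed variance. The size does: 82% to 100% significance for a pure drinking factor rests on assumed SDs, an effect of .01 per unit and driving unrelated to TAC. Where driving was somewhat less likely at higher TAC (log-odds −.1 per .01), part one turned negative (about −.09, significant in 46–59%) and part two stayed positive. The null-then-positive pattern is therefore possible, not certain.

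**What to change.** Keep part two, and describe its coefficient as *TAC level among drives, including general drinking level*. Add one supplementary analysis over all drinking events:

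- Model drove yes/no on the predictor, event TAC and TAC × predictor, with participant random effects. Enter TAC as a spline and centre it at a value fixed in advance.
- Define event TAC in advance and identically for driven and non-driven events. Event peak is one option, since drinking at home has no trip home. It differs from the part-two outcome, level at the time of driving, and the SAP should say so.
- Report the predictor's slope on TAC in non-driven events beside the drives-only slope. Treat the drove × predictor contrast as descriptive, not as the sole decision rule.
- Claim specificity only when the predictor is associated with driving at a given TAC.
- State the denominator of the .05 and .08 cutpoint models.

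The result remains an association, since an unmeasured influence on both drinking and driving could still contribute. The cost is SAP wording, one extra model on data already planned, a TAC definition to fix in advance, and probably somewhat less precision for the specificity claim than for the drives-only slope.

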AA024182 (PI [name]), ongoing work in the PI's lab is focused on developing multiple novel decision making tasks relevant to AID. The laboratory component of the project will include tasks from this line of research that are both associated with AID and sensitive to acute alcohol effects. Ambulatory Assessment The ambulatory assessment arm of the project will involve 6 weeks of data collection for all study participants. During this period, data will be collected via self-report (EMA), the BActrack Skyn (TAC), and location and movement data passively collected from the GPS and accelerometer of the smartphone. Participants will be randomly assigned to two Full AA groups and the MA control group. EMA. During their AA participation, participants will provide self-report data using a study-provided smartphone. Following previous research ([name] et al., 2008a), participants will attend initial orientation sessions to be trained in completing assessments. Participants will return to the lab every 7 days for a brief session to review compliance and receive interim payment, which has proven to increase compliance ([name] et al., 2008b). Participants will complete 5 reports per day – a morning report and 4 “evening” reports. The “evening” reports will be scheduled for 6pm, 8pm, 10pm, and midnight.

However, participants will be able to reschedule or self-initiate the reports if they are consuming alcohol (or using other substances) at other times. The morning report will be scheduled on an individual basis, 30 minutes after participant's self- reported standard waking time. If participants go to bed prior to the midnight assessment, they will

complete a final assessment and put the smartphone to “sleep”, which will terminate follow-up prompts. To

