
associations is .91 in the logistic model and .99 in the linear mixed model. If Aim 2 is realized, then we can only use half of the Full AA group (the half that does not receive AA for the first six weeks), along with the

MA control group, to assess raw associations between lower-level variables and AID. In this case, we estimate power of .85 and of .99 to detect the associations (using the same values as above with a reduced sample size). We computed additional power estimates for moderation Hypotheses 1.3, using both the logistic model (where AID is a binary DV) and the Gaussian model (where TAC/BrAC is the DV). We assumed that Aim 2 was not realized, reducing the overall number of participants that we could enter into the analysis. For the logistic model, we assumed (as above, based on pilot data) that each 5-point increase in impulsivity was associated with a 10% increase in the odds of driving after drinking. We further assumed that this relationship was moderated by drinking venue, such that the relationship was diminished when participants were drinking at a restaurant. Under this scenario, power was .77 for the moderation

effect. For the Gaussian model, we assumed (as we did above) that each 5-point increase in impulsivity was associated with a mean BrAC increase of .01. We further assumed that this relationship was moderated by drinking location, such that the relationship was absent if a person was drinking 10 or more miles from home. Under this scenario, power was .96 for the moderation effect. Aim 2. Test potential effects of AA on AID behavior and intentions. For Aim 2, the study design affords us multiple manners in which we can examine the potential of mobile technology as an intervention for AID. We can estimate the effect of AA prospectively, examining whether or not AID changes from before a participant receives AA to after. We can also estimate the effect across experimental groups, examining whether or not AID differs between the groups with Full AA and the MA control group. To address this question, we will again employ the two DVs of driving after drinking and TAC in separate GLMMs (where drinking events are nested within participants). The IVs in each model will be dummy variables that are related to each participant's condition and to the time within the study. Specifically, the dummy variables will reflect whether or not the

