individual is currently receiving AA, as well as whether or not the individual ever previously received AA. This will allow us to disentangle the effect of currently receiving AA from effects that may last after the individual has received AA. In computing power, we assumed 100 participants receiving AA at differing times (as described in Overview of Proposed Work) coupled with 100 participants in the control group. We further assumed that (i) active reception of AA reduces driving after Research Strategy Page 69 Contact PD/PI: [name] drinking from an average of twice per month to an average of 1.5 times per month (with individual differences in this effect), and (ii) active reception of AA reduces TAC of driving events by an average of .01. In employing assumption (i) in a logistic mixed model, we obtained a simulation-based power estimate of .79 to detect an intervention effect of active AA. In employing assumption (ii) in a Gaussian linear mixed model, we obtained a simulation-based power estimate of .97 to detect the intervention effect.

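### Aim 2 names two AA-status dummies but no study-period term, so a time trend shared by all arms would be read partly as a lasting AA effect

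*Combined protocol and SAP*

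**What the plan says.** Under Statistical Analyses and Power, Aim 2, driving after drinking and TAC are analysed in separate mixed models, with drinking events nested in participants. The predictors are introduced as dummies tied to each participant's "condition and to the time within the study". The next sentence specifies them: whether the "individual is currently receiving AA, as well as whether or not the individual ever previously received AA". The stated purpose follows: "This will allow us to disentangle the effect of currently receiving AA from effects that may last after the individual has received AA".

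The rest of the design comes from other places in the same document:

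- Ambulatory Assessment: "Participants will be randomly assigned to two Full AA groups and the MA control group". The same section says the "ambulatory assessment arm of the project will involve 6 weeks of data collection for all study participants".
- Aim 1 power text: one half of the Full AA group is "the half that does not receive AA for the first six weeks".
- Aim 2 power text: "100 participants receiving AA at differing times" and 100 controls. The timing itself is deferred to an Overview that is not in the supplied text.
- Aim 2 power results: for driving, a "power estimate of .79 to detect an intervention effect of active AA"; for TAC, .97. No power is given for the lasting effect.

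**The concern.** Both named dummies describe AA status. Time enters only through them. A participant can have previously received AA only after an AA block has ended, so that dummy is 1 only at later study times. MA controls are 0 on both dummies throughout, so their early and late events are pooled into one reference level. If driving after drinking drifts in every arm, for example because all arms report on their drinking several times a day, the pooled reference level does not follow the drift and the lasting-effect coefficient absorbs it.

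A decline that also occurs in MA controls could therefore be reported as an effect that persists after AA ends. Randomisation makes the shared trend estimable from concurrent groups, but the named terms do not use them for that. The two dummies alone cannot deliver the separation the plan claims.

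**Working it through.** **1. The plan's own figure.** The .79 cannot be reproduced: events per person, random-effect variances, alpha and the observation schedule are not given. Two drives per month at 15% of events (the Aim 1 assumption) implies 2/0.15 = 13.3 events per month, or about 18.4 per six weeks. A fall to 1.5 per month is 0.15 × 1.5/2 = 0.1125. With 100 v 100 participants, one six-week block, independent events and two-sided 5%, power is .92; a design effect of 1.5 gives .786. So .79 is attainable. Nothing here shows it, or .97, to be wrong.

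**2. Loading by hand.** Assumed layout: two six-week periods, 50 immediate AA, 50 delayed AA, 100 MA, all observed in both. There is no AA effect, and a shared trend of one unit in period 2. With uncorrelated observations the coefficients are differences of cell means:

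- Reference (0,0): delayed P1 (50, value 0), MA P1 (100, value 0), MA P2 (100, value 1). Mean 100/250 = 0.40.
- Current AA: immediate P1 (50, value 0), delayed P2 (50, value 1). Mean 0.50; loading 0.50 - 0.40 = 0.10.
- Previous AA: immediate P2 (value 1). Mean 1.00; loading 1.00 - 0.40 = 0.60.

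**3. With within-person correlation r.** Solving the GLS equations for the same layout gives intercept a = (4 - r - 3r²)/(10 + 2r - 4r²) and s = (1 + ra)/(2 - r²). The current-AA loading is s - a and the previous-AA loading is 1 - a + rs.

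| r | a | s | Current AA | Previous AA |
|---|---|---|---|---|
| 0 | 0.400 | 0.500 | 0.10 | 0.60 |
| 0.4 | 0.307 | 0.610 | 0.30 | 0.94 |
| 0.8 | 0.142 | 0.819 | 0.68 | 1.51 |
| limit 1 | 0 | 1 | 1 | 2 |

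With a period term the model fits this pattern exactly, so both loadings are 0.

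**4. Other schedules.** Six layouts were tried: the one above; MA in the first block only; MA split evenly over the blocks; a pre-period added; a follow-up period added; both added (linear trend in the last three). Intercept SD was 0.5-1.3, AA-slope SD 0-0.9, and events 10 or 18.4 per period. Previous AA loaded 0.7 to 2.4, positive in every layout. Current AA loaded -0.2 to 1.2, and 0.2 to 0.7 in the two-period layout with everyone observed. The sign for current AA depends on the schedule. With a follow-up period, a linear trend 0, 1, 2 and r = 0, the reference mean is 300/350 = 0.86 and the current-AA mean 0.50 (loading -0.36), while previous AA is 1.67 - 0.86 = 0.81.

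**5. False rejection in the driving model.** Logistic mixed model by maximum likelihood, random intercept and random AA slope, the step 2 layout, baseline 15% of events, no AA effect, Wald tests at 5%, 400 runs per scenario. Intercept SD / slope SD / events per period: 0.7/0.3/13.8, 1.0/0.3/15.2, 1.0/0.6/12.4. Events were set below 18.4 to aim at the plan's .79 (achieved .81-.85).

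| Shared decline, drives per month | Previous AA | Current AA |
|---|---|---|
| 2.0 to 1.9 | 5.5-7% | 5-6% |
| 2.0 to 1.75 | 15-20% | 6.5-8.5% |
| 2.0 to 1.5 | 48-68% | 13-28% |

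With a period term all rates are 4-6.5%. Monte Carlo SE is about 1 point at 5% and up to 3 points elsewhere. The previous-AA rate reaches 10% when loading × trend / SE = 0.65, which is a decline to about 1.83-1.86. That is 0.14-0.17 of the plan's assumed 0.5 fall, or roughly a third.

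A separate simulation (random intercept only, SD 0.5, 1.0, 1.5; shared odds ratio 0.75) gave 47%, 62% and 67% for previous AA and 14%, 28% and 35% for current AA. With a period term these fell to about 3-6% and 6-8%.

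**The case against.** The strongest reply is that the omission is inferred. The plan mentions time within the study, gives no model equation, and its list may describe how AA status is coded rather than every term in the model. That stands as a reason to ask first. It does not settle the matter, because the sentence that specifies the dummies contains no period term and the claim of separation rests on those dummies.

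The schedule sits in an Overview that was not supplied, so every layout and multiplier here is assumed. The six-week statement leaves it unclear whether MA controls are seen in both periods, and false-rejection rates were computed only for the layout where they are. The loading range also moves outside the six layouts: 0.60 under working independence, and 0.44-1.37 if MA data exist only in the second block. In none of these does the sign for previous AA change.

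The trend is hypothetical. A small one does little harm, and the 48-68% needs a shared decline as large as the whole assumed AA effect. The coefficient mainly affected is not the one the plan powers. Both points are right and limit the weight of the concern, but the plan neither rules a trend out nor protects against one.

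Last, a period term can be expensive if MA controls supply one block only. That stands, and it is why the schedule has to be stated with the model.

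**Conclusion.** The concern holds. On the terms as named, a trend common to all arms loads on the lasting-effect coefficient, by 0.7 to 2.4 times the per-period trend in the six layouts, and the plan cannot separate the two. The damage is slight for a shared decline to 1.9 drives per month, doubles the nominal error at about 1.83-1.86, and is serious at 1.75 or below.

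No firm claim is made about current AA, and the stated powers are not shown to be wrong; they hold for a two-dummy analysis only if there is no shared trend. Variances, schedules and trend sizes are assumptions, so the direction for previous AA is firm and the exact rates are illustrative. This should be fixed before analysis; confidence is medium because the schedule and any intended period term are not visible.

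**What to change.** - State whether a study-period term is in both Aim 2 models. If not, add study period (first or second six weeks, or week in study) as a fixed effect in both, so that concurrent MA controls and the delayed group estimate the shared trend.
- State which weeks MA controls contribute to each outcome.
- Re-run the .79 and .97 power simulations with the period term.
- If TAC exists only in monitored weeks, say that the lasting-effect term does not apply to the TAC model.

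This is SAP wording and one model term, with no new data. The price is power in the driving model:

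| Driving-model power | Two dummies | With period term |
|---|---|---|
| Current AA, MA in both periods (three settings) | .845, .842, .835 | .83, .785, .802 |
| Current AA, MA one block, split evenly | .84 | .71 |
| Current AA, MA all in first six weeks | .86 | .45 |
| Lasting effect of the same size (2.0 to 1.5) | .44-.54 | .35-.44 |

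The one-block rows use the 1.0/0.3 setting only; they and the lasting-effect row rest on 300 runs each. If MA controls turn out to supply the first block only, that loss should be faced at the design stage, because the two-dummy power avoids it only by assuming there is no trend.
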